### 6.1.2 Disease Parameters

**Measurable Disease:** Tumor lesions: Must be accurately measured in at least one dimension (longest diameter in the plane of measurement is to be recorded) with a minimum size of:

1. 10 mm by CT scan (CT scan slice thickness no greater than 5 mm)
2. 10 mm caliper measurement by clinical exam (lesions which cannot be accurately measured with calipers should be recorded as non-measurable)
3. 20 mm by chest x-ray.

Non-measurable disease.

All other lesions are considered non-measurable, including small lesions (longest diameter < 10mm or pathological lymph nodes with  $\geq 10$  to < 15 mm short axis) as well as truly non-measurable lesions. Lesions considered truly non-measurable include: leptomeningeal disease, ascites, pleural or pericardial effusion, inflammatory breast disease, lymphangitic involvement of skin or lung, abdominal masses/abdominal organomegaly identified by physical exam that is not measurable by reproducible imaging techniques.

Target lesions.

All measurable lesions up to a maximum of five lesions total (and a maximum of two lesions per organ) representative of all involved organs should be identified as target lesions.

All measurable lesions should be recorded and measured at baseline. A sum of the longest diameter (LD) for all target lesions will be calculated and reported as the baseline sum LD. The baseline sum LD will be used as reference by which to characterize the objective tumor response.

Non-target lesions. All other lesions (or sites of disease) including any measurable lesions over and above the five target lesions should be identified as **non-target lesions** and should also be recorded at baseline. Measurements of these lesions are not required, but the presence or absence of each should be noted throughout follow-up.

### 6.1.3 Methods for Evaluation of Measurable Disease

All measurements should be taken and recorded in metric notation using a ruler or calipers. All baseline evaluations should be performed as closely as possible to the beginning of treatment and never more than 28 days before the beginning of the treatment planning session.

The same method of assessment and the same technique should be used to characterize each identified and reported lesion at baseline and during follow-up. Imaging-based evaluation is preferred to evaluation by clinical examination when both methods have been used to assess the antitumor effect of a treatment.

Conventional CT with contrast: These techniques should be performed with cuts of 1 mm or less in slice thickness contiguously. Spiral CT should be performed using a 5 mm contiguous reconstruction algorithm.

MRI: Will be performed with gadolinium if possible. These techniques should be performed with cuts of 1 mm or less in slice thickness contiguously.

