## **2.4 Endpoints**

### **2.4.1 Primary Endpoint:**

Local control of the SRMs will be defined as <4mm increase in the longest tumor diameter compared to pre-treatment scan on an MRI or contrast-enhanced CT scan in the setting of no radiographic or pathologic evidence of viable tumor.

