##### **4.1.1.2 Effective Delineation of Targets**

The edge of the intended target should be distinct from uninvolved normal tissue such that there is little need for expansions for subclinical extension or uncertainty. A variety of appropriate imaging can be used to define targets clearly so long as these imaging platforms can be accurately and reliably “fused” with the planning data set and brought into the context of stereotactic targeting conveyed in the next paragraph. Patient’s baseline MRI will be fused to the planning CT (preferably with IV contrast if patient is able to tolerate) for this purpose whenever applicable.

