**5.0 STUDY PROCEDURES****5.1 Screening/Baseline Procedures**

Assessments performed exclusively to determine eligibility for this study will be done only after obtaining informed consent. Assessments performed for clinical indications (not exclusively to determine study eligibility) may be used for baseline values even if the studies were done before informed consent was obtained.

All screening procedures must be performed within two months prior to registration unless otherwise stated. The screening procedures include:

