**5.2 Procedures during Treatment**

SABR treatment will be delivered either in three, four or five fractions. For a given lesion (target), a minimum of 40 hours and a maximum of 8 days should separate consecutive treatments. All treatment must be completed within 21 days.

**5.2.1 Prior to starting first SABR treatment: Baseline assessment is sufficient and need not be repeated if done within the past two months**

- Physical exam, vital signs

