**5.4 Time and Events Table**

	Pre-study Within 2 months prior to registration	Day 1 First SABR	At One month (+/- 1 week)	q6 Months (+/- 2 weeks)	At one year (+/- 2 weeks)
Assessment	X				
Informed Consent	X				
Diagnostic/ Pre- treatment Renal Bx	X				
Post-treatment Renal Bx					X
Physical Exam	X	X	X	X	
Performance Status	X		X	X	
Toxicity Evaluations			X	X	
Tumor Measurements	X			X	

Chemistry	X		X	X	
CBC	X		X	X	
Correlative Labs	X	X*	X*	X*	
Urine Analysis	X		X	X	
MRI or CT	X			X	
Renal Scan	X				X

\*Correlative labs will be drawn at baseline, on first day of SABR (see section 8), at one month and at 6 month after SABR.

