#### **6.1.4 Response Criteria**

##### **6.1.4.1 Evaluation of Lesions**

Complete Response (CR): Disappearance of all target lesions. Disappearance of all target lesions. Any pathological lymph nodes (whether target or non-target) must have reduction in short axis to <10 mm (the sum may not be "0" if there are target nodes). Determined by two separate observations conducted not less than 4 weeks apart. There can be no appearance of new lesions.

Partial Response (PR): At least a 30% decrease in the sum of the longest diameter (LD) of target lesions, taking as reference the baseline sum LD. There can be no appearance of new lesions.

Progressive Disease (PD): > 20% increase in the SLD taking as reference the smallest SLD recorded since the treatment started (nadir) and minimum 5 mm increase over the nadir.

Stable Disease (SD): Neither sufficient shrinkage to qualify for PR nor sufficient increase to qualify for PD, taking as reference the smallest sum LD since the treatment started. There can be no unequivocal new lesions.

Tumor Growth (TG): At least a 4mm increase in the LD of treated lesion in a single scan when compared to baseline scan (or an increase of >2.0mm in two consecutive scans).

Local Control: No TG AND a complete radiographic or pathologic absence of tumor viability.

Local Failure: Any TG OR any radiographic or pathologic evidence of tumor viability.

Indeterminate Disease Response: (IDR): 1) Presence of radiographic evidence of viable disease without any increase in the LD (<4mm) sufficient enough to qualify for TG; 2) complete absence of radiographic evidence of viable disease regardless of any change in tumor diameter.

A biopsy is recommended in the case of tumors with ≥4mm increase in size with no radiographic evidence of viable tumor, OR any tumors with radiographic evidence of viable tissue.

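### The calendar lets the baseline tumour scan be two months old at registration, while 6.1.3 limits it to 28 days before planning; the reference diameter for local control and growth rate needs one window and one anchor

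*Protocol*

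**What the plan says.** Two rules cover the age of the baseline tumour scan.

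- Section 5.1: "All screening procedures must be performed within two months prior to registration unless otherwise stated". The Time and Events Table (5.4) marks both MRI or CT and tumour measurements under "Within 2 months prior to registration", with no footnote on either row. Section 5.1.15, the tumour-assessment item, gives no shorter window and does not refer to 6.1.3.
- Section 6.1.3: baseline evaluations should be as close as possible to the start of treatment and "never more than 28 days before the beginning of the treatment planning session".

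The rules differ in length (two months against 28 days) and in anchor (registration against planning session). The protocol states no maximum time from registration to planning, or from planning to the first fraction.

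The scan is the reference for three outcomes. Local control (2.4.1) requires "<4mm increase in the longest tumor diameter compared to pre-treatment scan", together with no evidence of viable tumour. Tumor Growth (6.1.4.1) is "At least a 4mm increase in the LD of treated lesion in a single scan when compared to baseline scan"; the same definition adds a second route, met by a smaller rise that is seen twice (more than 2.0 mm on consecutive scans). Growth rate (2.4.2.2) is compared with baseline and expressed in cm/year. No section says which scan is meant if a patient has more than one before treatment.

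**The concern.** Inclusion criterion 3.1.4 requires more than 2 mm of growth within a year, so these tumours are selected because they are growing. Whatever a tumour gains between the reference scan and the first fraction is included in the later increase in diameter, although SABR could not have prevented it. The direction is predictable: local control is pushed down and the post-treatment growth rate up, by an amount that depends on scheduling.

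A scan taken 50 days before registration satisfies the calendar. If planning follows registration, as one would expect, the same scan breaches 6.1.3. Staff working from the table would not see the 28-day limit, so reference diameters of different ages could enter a 16-patient dataset unnoticed.

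**Working it through.** **Inputs from the protocol.** Untreated growth: 0.4 cm/year for biopsy-confirmed RCC and 0.28 cm/year for all small renal masses (1.3). Planned comparison: 0.4 against 0.16 cm/year, SD 0.36 cm/year, n = 16, two-sided 0.10, 80% power; expected local control at least 90% with standard error at most 7.5% (9.2). Thresholds: 4 mm and 2.0 mm (6.1.4.1).

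**Assumptions.** Linear growth; two months = 61 days; only the two stated windows are compared. Actual scan-to-SABR intervals are not given.

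**Step 1: the plan's own figures.** Standard error = √(0.9 × 0.1/16) = 7.5%, as stated. One-sample t-test: noncentrality = (0.24/0.36) × √16 = 2.667 with 15 df, giving power of 81.6%, consistent with the stated 80%.

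**Step 2: untreated growth in each window** = rate × days/365.25.

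| Rate (cm/year) | 28 days | 61 days |
|---|---|---|
| 0.28 | 0.21 mm | 0.47 mm |
| 0.40 | 0.31 mm | 0.67 mm |
| 0.76 (0.4 + 1 SD) | 0.58 mm | 1.27 mm |
| 1.12 (0.4 + 2 SD) | 0.86 mm | 1.87 mm |

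At 0.4 cm/year this is 8% and 17% of the 4 mm limit, and 15% and 33% of the 2.0 mm limit. The last two rows borrow the SD assumed for the t-test, which the protocol does not describe as the SD of untreated growth; they show a range only. At 0.4 cm/year, untreated growth alone would need about 365 days to reach 4 mm.

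**Step 3: local control, size component only.** Take the one-year change as normal with SD 0.36 cm, and set its mean so that 90% of patients stay below 4 mm: 0.4 − 1.2816 × 0.36 = −0.061 cm. Add the untreated growth at 0.4 cm/year.

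| Gap | Added | P(increase ≥ 4 mm) | Expected in 16 |
|---|---|---|---|
| none | 0 | 10.0% | 1.60 |
| 28 days | 0.031 cm | 11.6% | 1.85 |
| 61 days | 0.067 cm | 13.7% | 2.18 |

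The difference between the windows is about 2 points, or 0.3 of 16 patients. If the mean is instead the protocol's 0.16 cm, the probabilities are 25.3%, 28.1% and 31.5%: about 3.5 points, or 0.55 of 16 patients, between the windows.

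**Step 4: growth rate over one year after SABR.** The size of the effect depends on when the clock starts, which 2.4.2.2 does not settle.

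| Gap | Rate, time from SABR | Power | Rate, time from scan | Power |
|---|---|---|---|---|
| none | 0.160 | 82% | 0.160 | 82% |
| 28 days | 0.191 | 72% | 0.177 | 76% |
| 61 days | 0.227 | 58% | 0.194 | 70% |

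Example at 61 days: from SABR, 0.16 + 0.067 = 0.227 cm/year; from the scan, 0.227/(1 + 61/365.25) = 0.194 cm/year. Power uses the Step 1 formula with the difference from 0.4 reduced accordingly.

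**The case against.** The strongest reply is that the text largely resolves itself. Section 5.1 sets two months only where nothing else is stated, and 6.1.3 states something else in mandatory terms for exactly this evaluation. The table column also behaves like a default: the pre-treatment biopsy sits in it, yet 5.1.14.1 accepts a biopsy up to a year old. Because the anchors differ, one scan can satisfy both rules. A two-month-old reference scan is then a deviation from 6.1.3, not something the plan clearly permits. This stands, and it limits the point to an inconsistency that can mislead. It does not remove it, since neither the table nor 5.1.15 points to 6.1.3.

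It is also fair that any pre-treatment scan admits some untreated growth, including under the 28-day rule. Only the increment between the windows, under 0.4 mm at 0.4 cm/year, belongs to the discrepancy.

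Three stronger readings are tempting, but the documents do not support them.

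- A reader might infer from 5.2.1 ("Baseline assessment is sufficient and need not be repeated if done within the past two months") that an old scan need not be repeated. That item lists only physical examination and vital signs.
- A reader might infer, because the "baseline MRI will be fused to the planning CT", that the target is drawn on outdated anatomy. Section 4.5.1 makes CT the primary platform for targeting, fusion applies only where applicable, and 4.5.2 adds margins of 0.5 and 1.0 cm.
- A reader might add registration-to-planning and planning-to-SABR delays to reach three months or more. At 89 and 122 days, untreated growth at 0.4 cm/year would be 1.0 and 1.3 mm, but those delays are assumptions. The protocol neither reports nor limits them.

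**Conclusion.** The inconsistency is real and of low to moderate importance. The calendar and 6.1.3 give different windows and anchors for the scan that supplies the reference diameter, and the cross-reference that would settle the matter is missing.

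For local control the consequence is small and conservative: about 2 percentage points between the windows if 90% control is expected, and about 3.5 if the mean one-year change is 0.16 cm. In both cases apparent failures are added. A reader might infer that the primary result is seriously biased; these figures do not show that, and they leave aside the viability component of the endpoint.

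The growth-rate comparison is more exposed. Power falls from about 82% to 58–70% with a two-month-old scan, against 72–76% with a 28-day-old scan. Section 9.3 plans descriptive statistics for growth rate, so the power figures mainly indicate how far the estimate would move: from 0.16 to between 0.19 and 0.23 cm/year at two months.

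The results rest on linear growth at 0.4 cm/year, a normal model with the protocol's SD, and gaps equal to the stated windows. The 2.0 mm two-scan criterion could be affected proportionally more, but 2.4.1 does not include it and 6.1.4.1 does not make its reference scan explicit.

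**What to change.** 1. Reconcile 5.1.15, 5.4 and 6.1.3 so that the tumour-measurement scan has one window and one anchor. One way is a footnote to the MRI or CT and tumour-measurement rows carrying the limit that 6.1.3 already imposes, leaving two months for the other screening items.
2. State that this scan is the pre-treatment scan of 2.4.1 and the baseline scan of 6.1.4.1, and which scan counts if there are several.
3. Record the scan and first-fraction dates and compute growth rates from actual scan dates, stating where the clock starts. If the statistical analysis plan already does this, a cross-reference is enough.
4. For patients already enrolled, report the scan-to-SABR gap beside the local control and growth-rate results.

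The cost is a footnote and a few sentences in an amendment, and an occasional repeat scan for a patient whose imaging is too old, which 6.1.3 already requires.

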#### **6.1.4 Response Criteria**

##### **6.1.4.1 Evaluation of Lesions**

Complete Response (CR): Disappearance of all target lesions. Disappearance of all target lesions. Any pathological lymph nodes (whether target or non-target) must have reduction in short axis to <10 mm (the sum may not be "0" if there are target nodes). Determined by two separate observations conducted not less than 4 weeks apart. There can be no appearance of new lesions.

Partial Response (PR): At least a 30% decrease in the sum of the longest diameter (LD) of target lesions, taking as reference the baseline sum LD. There can be no appearance of new lesions.

Progressive Disease (PD): > 20% increase in the SLD taking as reference the smallest SLD recorded since the treatment started (nadir) and minimum 5 mm increase over the nadir.

Stable Disease (SD): Neither sufficient shrinkage to qualify for PR nor sufficient increase to qualify for PD, taking as reference the smallest sum LD since the treatment started. There can be no unequivocal new lesions.

Tumor Growth (TG): At least a 4mm increase in the LD of treated lesion in a single scan when compared to baseline scan (or an increase of >2.0mm in two consecutive scans).

Local Control: No TG AND a complete radiographic or pathologic absence of tumor viability.

Local Failure: Any TG OR any radiographic or pathologic evidence of tumor viability.

Indeterminate Disease Response: (IDR): 1) Presence of radiographic evidence of viable disease without any increase in the LD (<4mm) sufficient enough to qualify for TG; 2) complete absence of radiographic evidence of viable disease regardless of any change in tumor diameter.

A biopsy is recommended in the case of tumors with ≥4mm increase in size with no radiographic evidence of viable tumor, OR any tumors with radiographic evidence of viable tissue.

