showing growth >2mm in two scans will be enrolled and treated with SABR in this trial. The primary endpoint in this trial is local control and the hypothesis tested is that SABR to the SRMs will lead to an elimination of tumor growth. The local control will be defined using MRI or contrast CT and <4mm increase in single scan or <2.0mm increase in two different scans in the setting of an absence of radiographic indication of tumor viability will constitute local control [56]. Kidney function will be monitored closely to evaluate radiation induced kidney toxicity.

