### 6.1.1 Definitions

Evaluable for toxicity. All subjects will be evaluable for toxicity from the time of their first treatment with SABR.

Evaluable for objective response. Only those subjects who have measurable or non-measurable disease present at baseline, have received ALL fractions of SABR and have had their disease re-evaluated with a minimum of one year of follow up will be considered evaluable for response. These subjects will have their response classified according to the definitions stated below.

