## 9.0 STATISTICAL CONSIDERATIONS

### 9.1 Study Design/Study Endpoints

This is an open label single-arm phase II non-randomized prospective single arm study that treats a single SRM with SABR. The primary objective is local control of the SRMs. Local control is defined as less than 4mm increase in the longest diameter of tumor measured using either MRI or contrast enhanced CT scan and with no radiographic or pathologic evidence of viable tumor. The endpoint will be measured at a minimum follow up of one year. Secondary objections and endpoints explore the safety, toxicity, growth, growth rate, local failure, IDR, immune response and progression of the SRMs after SABR.

The stopping rules for this study include any treatment-related >grade 3 toxicity. If there are any treatment related grade 3 acute toxicity in >30% of enrolled patients after enrollment of at least 6 patients, the study will be suspended until permitted by a safety review.

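### The size part of local control is defined differently across sections of the protocol, and its assessment time is only a one-year minimum

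*Protocol*

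**What the plan says.** The protocol gives the size criterion in four places.

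- **Section 2.4.1 (primary endpoint):** "<4mm increase in the longest tumor diameter compared to pre-treatment scan", with no two-scan clause.
- **Section 9.1 (statistics):** "Local control is defined as less than 4mm increase in the longest diameter of tumor", again with no two-scan clause.
- **Section 6.1.4.1 (response criteria):** tumor growth (TG) means at least 4 mm "in a single scan when compared to baseline scan (or an increase of >2.0mm in two consecutive scans". This binds the primary endpoint, because the same section states "Local Control: No TG AND a complete radiographic or pathologic absence of tumor viability" and makes any TG a local failure.
- **Section 1.3 (rationale):** control is "<4mm increase in single scan or <2.0mm increase in two different scans", together with no radiographic sign of viable tumour.

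On timing, 9.1 says "The endpoint will be measured at a minimum follow up of one year". Section 6.1.1 requires that patients "have had their disease re-evaluated with a minimum of one year of follow up will be considered evaluable for response". Both set a floor and neither names a time point. Section 4.11 plans 2 to 5 years of follow-up, and 5.3 plans six-monthly visits with imaging for five years. Section 4.13 allows replacement of patients who withdraw, are lost or refuse scans if they have fewer than three follow-up scans or less than a year of follow-up. Section 9.3 estimates the local control rate as a proportion with an exact binomial interval and attaches no time to it.

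**The concern.** The primary endpoint is a yes/no classification in 16 patients. If two sections classify the same patient differently, someone has to choose between them, possibly after the scans have been read. The growth definition also bears on the proportion of patients without growth (9.3), the growth comparison used for power (9.2) and the growth criterion in the stopping rule (7.4).

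The open assessment time adds a second freedom. A fixed millimetre limit against a fixed baseline gives a slowly growing lesion more chances to fail the longer it is scanned. A crude proportion over patients with unequal follow-up would then depend partly on accrual timing and the data cut-off.

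**Working it through.** **The plan's own precision.** Section 9.2 has N = 16 and expects control of at least 90%. The standard error is √(0.9 × 0.1 / 16) = 7.5%, and 1.96 × 7.5% = 14.7%, which matches the stated 7.5% and 15%. These figures are not at fault. One reclassified patient moves the rate by 1/16 = 6.25 points: 15/16 has an exact 95% interval of 69.8% to 99.8%, and 14/16 has 61.7% to 98.4%.

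**One lesion under each rule.** Take +3 mm over baseline on two consecutive scans, with no viable tumour.

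| Rule | Status |
|---|---|
| 2.4.1 and 9.1 | Controlled (3 < 4) |
| 6.1.4.1, 2.0 mm measured from baseline | Local failure (3 > 2.0 twice) |
| 6.1.4.1, 2.0 mm measured from the previous scan | Controlled (second increase is 0) |
| 1.3, *or* read literally | Controlled |
| 1.3, both limits required | Not controlled |

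The rules disagree only for increases of more than 2.0 mm and less than 4 mm seen on two scans. For 6.1.4.1 the unnamed reference scan decides the outcome. If increases are measured scan to scan, two successive rises above 2.0 mm from baseline already total more than 4 mm, so at 12 months, with only two scheduled follow-up scans, the clause adds nothing.

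**Dependence on time, no measurement error.** At 0.16 cm/year (the post-treatment rate in the 9.2 growth-rate test), a lesion reads +0.8, +1.6, +2.4, +3.2 and +4.0 mm at 6, 12, 18, 24 and 30 months. It is controlled at 12 months under every rule. It fails at 24 months under 6.1.4.1 measured from baseline (2.4 then 3.2), but only at 30 months under 2.4.1 and 9.1.

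**Dependence on time, with measurement error.** This is a simulation of 300,000 lesions per scenario with six-monthly scans, linear growth and independent normal error on baseline and follow-up scans. A lesion fails if it breaks the rule at any scan so far. The two-scan clause is measured from baseline. The error SDs are assumptions; the protocol gives none.

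| Growth, error SD | Rule | 1 y | 2 y | 3 y | 5 y |
|---|---|---|---|---|---|
| 0, 0.5 mm | 4 mm only | 100% | 100% | 100% | 100% |
| 0, 0.5 mm | with two-scan clause | 100% | 100% | 99.9% | 99.9% |
| 0, 1.5 mm | 4 mm only | 94% | 90% | 87% | 83% |
| 0, 1.5 mm | with two-scan clause | 91% | 84% | 79% | 73% |
| 1.6 mm/y, 1.0 mm | 4 mm only | 94% | 64% | 19% | 0% |
| 1.6 mm/y, 1.0 mm | with two-scan clause | 85% | 39% | 6% | 0% |

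These are size-only control rates. They never rise with follow-up, and the drop ranges from nothing to almost everything.

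**Replacement criterion.** Six-monthly scanning gives two follow-up scans by month 12 and a third at month 18. A patient with a complete 12-month assessment who then refuses scans still falls under the three-scan criterion in 4.13.

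**The case against.** Three objections have force.

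**The conflict depends on a reading.** A reader might infer that 6.1.4.1 plainly fails the +3 mm lesion, or that the protocol holds three irreconcilable rules. The text supports neither. Measured scan to scan, the two-scan clause has almost no effect, and 1.3 may be a loose complement of 6.1.4.1. What stands is that 6.1.4.1 does not say which reading applies, that 2.4.1 and 9.1 omit the clause altogether, and that 1.3 uses *different* scans where 6.1.4.1 uses *consecutive* ones.

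**The time effect can be overstated.** Applying the growth rate of 0.16 cm/year with SD 0.36 from 9.2, and assuming linear growth and normal rates, P(rate < 0.4/T) is 75% at T = 1 year, 54% at 2 and 41% at 5. The arithmetic is right, but it does not forecast this endpoint. Those inputs are the alternative for the growth-rate t-test, a secondary endpoint, and the same section expects control of at least 90%. Extending each patient's rate linearly to five years is an added assumption.

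**A 12-month landmark may be intended.** The mandatory one-year biopsy and the one-year evaluability floor point that way, and a data cut-off can be left to an analysis plan. But no section states a landmark, and the longer follow-up and the three-scan criterion point elsewhere.

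Nor does it follow that the result would fail a comparison with a benchmark. Section 9.2 says reliable historical data are lacking and justifies the local control rate by precision, without a null for it.

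**Conclusion.** The primary endpoint is inconsistent as written. Sections 2.4.1 and 9.1 use 4 mm alone, while 6.1.4.1 adds a two-scan clause with no reference scan. If that clause is measured from baseline, each patient with more than 2.0 but less than 4 mm on two consecutive scans and no viable tumour changes status, at 6.25 points per patient. If it is measured scan to scan, the practical difference at 12 months is nil.

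The assessment time is a floor only, so a crude proportion can depend on length of follow-up. The direction is clear, but the size rests on assumed growth and measurement error, and no single figure can be given. The stated sample size, standard error and power are unaffected.

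**What to change.** 1. State one size rule in identical words in 1.3, 2.4.1, 6.1.4.1 and 9.1, and name the scan from which each increase is measured. Report the other rule, with its own named reference scan, as a sensitivity analysis.
2. Fix one assessment time for the binomial rate. The 12-month scan and biopsy visit would fit the existing schedule. Say whether a breach at the 6-month scan counts.
3. Align the three-scan replacement criterion in 4.13 with that time, since only two follow-up scans are scheduled by month 12.
4. Add time to local failure to the Kaplan-Meier analyses in 9.3. These now cover time to progression, progression-free survival and overall survival. Progression in 2.4.2.3 is defined by stage, so they would not capture local failure by the millimetre rule.

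This is a wording amendment with no change to N = 16 or to the visits. The cost is that failures after the fixed time leave the primary rate and appear in a secondary summary.

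### Local Control, Local Failure and Indeterminate Disease Response overlap in Section 6.1.4.1, and the primary endpoint is not worded the same way across the protocol

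*Protocol*

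**What the plan says.** Section 6.1.4.1 of the protocol sets these definitions:

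- **Tumor Growth (TG):** "At least a 4mm increase in the LD of treated lesion in a single scan when compared to baseline scan", with a second limb, "or an increase of >2.0mm in two consecutive scans".
- **Local Control (LC):** "No TG AND a complete radiographic or pathologic absence of tumor viability".
- **Local Failure (LF):** "Local Failure: Any TG OR any radiographic or pathologic evidence of tumor viability".
- **IDR, limb 1:** "Presence of radiographic evidence of viable disease without any increase in the LD (<4mm) sufficient enough to qualify for TG".
- **IDR, limb 2:** "complete absence of radiographic evidence of viable disease regardless of any change in tumor diameter".

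No order of precedence is given. The section recommends a biopsy for growth of 4 mm or more without radiographic viability, and for any radiographic viability. It does not say how the result settles the category.

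The primary endpoint is also worded elsewhere. Section 2.4.1 requires an increase below 4 mm "in the setting of no radiographic or pathologic evidence of viable tumor", and Section 9.1 has the same content. Section 1.3 gives two growth limits joined by *or* (below 4 mm in one scan, below 2.0 mm in two scans) and asks only for the absence of radiographic viability; biopsy is not mentioned.

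LF and IDR are a secondary objective (2.2.10) and a secondary endpoint (2.4.2.6), both by reference to Section 6.1.4. Every patient is to have a biopsy at one year (5.1.14.2, 6.2). Section 9.3 estimates the local control rate with an exact binomial 95% interval.

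**The concern.** Outcome labels used for a primary rate and for secondary tabulations should place each patient once. Here a patient whom nobody would call indeterminate (no growth, clean imaging, clean biopsy) meets IDR limb 2, and every IDR limb 1 patient is already a failure.

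The Local Control sentence in 6.1.4.1 also accepts radiographic *or* pathologic absence of viability, while 2.4.1 and 9.1 exclude a patient with either kind of evidence. With imaging every six months and a one-year biopsy for everyone, disagreement between the two is a foreseeable result. In an open-label single-arm trial of 16 patients, the wording that governs should be fixed before the data are seen.

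**Working it through.** **The plan's own figure.** Section 9.2 gives n = 16 and an expected control rate of at least 90%. SE = √(0.9 × 0.1 / 16) = 0.075, and 1.96 × 0.075 = 0.147. This reproduces the stated 7.5% and 15%. That calculation is not in dispute; it serves as a yardstick below.

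**Step 1: label every combination.** The rules are those of 6.1.4.1, with growth (TG), radiographic viability (Rad) and pathologic viability (Path) each absent (−) or present (+). *LC inclusive* means that either absence suffices. *LC strict* means that both are required, as in 2.4.1 and 9.1.

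| TG | Rad | Path | LC inclusive | LC strict | LF | IDR |
|---|---|---|---|---|---|---|
| − | − | − | yes | yes | no | yes (limb 2) |
| − | − | + | yes | no | yes | yes (limb 2) |
| − | + | − | yes | no | yes | yes (limb 1) |
| − | + | + | no | no | yes | yes (limb 1) |
| + | − | − | no | no | yes | yes (limb 2) |
| + | − | + | no | no | yes | yes (limb 2) |
| + | + | − | no | no | yes | no |
| + | + | + | no | no | yes | no |

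- Inclusive reading: 4 cells carry two labels, 2 carry three and 2 carry one.
- Strict reading: 6 cells carry two labels and 2 carry one. LC and LF become exact complements (1 cell against 7), but IDR still overlaps one or the other in 6 cells.
- Imaging alone, without a biopsy result: 3 of 4 combinations carry two labels.

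So 6 of 8 combinations have more than one label on either reading. The reading of *or* changes LC status in 2 cells only: no growth, with imaging and biopsy in disagreement.

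**Step 2: compare the Local Control wordings.**

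| Patient | 1.3 | 2.4.1 and 9.1 | 6.1.4.1 |
|---|---|---|---|
| No growth, Rad −, Path + | control | not control | failure; also control if *or* is inclusive |
| No growth, Rad +, Path − | not control | not control | failure; also control if *or* is inclusive |
| +3 mm on two consecutive scans, no viability | depends on its own *or* | control (3 < 4) | TG (3 > 2.0), so failure |

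The last row takes the two-scan limb as measured against baseline. If it meant scan-to-scan steps, two steps from baseline would total more than 2.0 + 2.0 = 4.0 mm. The limb would then add something only for a tumour that had first shrunk.

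**Step 3: size.** One patient is 1/16 = 6.25 points. The protocol gives no discordance rate, so the following counts are assumptions. Take one clear failure and 15 patients without growth, of whom d are imaging-positive and biopsy-negative and the rest are clear successes. The strict rate is (15 − d)/16; the inclusive rate stays at 15/16 = 93.75%.

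| d | Strict rate | Gap to inclusive |
|---|---|---|
| 0 | 15/16 = 93.75% | 0 |
| 1 | 14/16 = 87.5% | 6.25 points |
| 2 | 13/16 = 81.25% | 12.5 points |
| 3 | 12/16 = 75% | 18.75 points |

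At d = 3 the exact 95% intervals are 47.6% to 92.7% (12/16) and 69.8% to 99.8% (15/16). The gap then exceeds the 14.7-point half-width.

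**The case against.** The strongest reply is that the primary endpoint has a home. Section 2.4.1 carries that heading, 9.1 repeats its content, and the Local Failure sentence in 6.1.4.1 agrees with both. All three make the two discordant no-growth cells not controlled. Only the 6.1.4.1 Local Control sentence departs from them, and only if its *or* is inclusive. This stands. A reader might infer from the triple labels that the primary endpoint is undetermined for discordant patients; the documents do not support that. Four of the six multi-label cells have the same control status on either reading of that sentence.

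A reader might also infer that IDR patients could be dropped, so that 12 controlled and 1 failed would give 12/13 = 92%. Nothing in the protocol removes them: the evaluability rule in 6.1.1 and the replacement criteria in 4.13 do not mention IDR.

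Nor does the biopsy recommendation in 6.1.4.1 show a plan for disagreement between imaging and biopsy. Its triggers are defined by growth and imaging, and a non-growing tumour with clean imaging and a positive biopsy is outside them.

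Finally, how a secondary category is analysed may be left to an SAP. But these definitions stand in the protocol and conflict there.

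**Conclusion.** The concern holds in two parts.

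1. The labels in 6.1.4.1 overlap in 6 of 8 combinations however *or* is read. IDR limb 1 is a subset of Local Failure, and limb 2 includes the unambiguous success. Local Failure and IDR therefore cannot be reported as distinct secondary outcomes.
2. The primary endpoint is stated inconsistently across four sections: on the role of pathology (1.3 against the rest), on discordant imaging and biopsy (6.1.4.1 on the inclusive reading against 2.4.1 and 9.1), and on the two-scan growth limb (6.1.4.1 against 2.4.1 and 9.1).

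The protocol does not say which section governs, but 2.4.1 and 9.1 supply a workable rule. This is a contradiction to remove, not an absent endpoint. The effect is 6.25 points per reclassified patient. Anything larger, such as 75% against 94%, rests on an assumed number of discordant patients.

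**What to change.** State one Local Control definition and use it identically in Sections 1.3, 2.4.1, 6.1.4.1 and 9.1: no tumour growth, and no radiographic evidence of viability, and no pathologic evidence of viability. Give one growth criterion that says whether the two-scan limb applies and against which scan it is measured. Make Local Failure the exact complement among evaluable patients.

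Redefine IDR as a descriptive sub-label of Local Failure for discordant findings: radiographic viability without growth, growth without radiographic viability, or imaging and biopsy that disagree. It should never include a patient with no growth and no viability, and never leave the denominator. Of the 8 combinations, 1 is then control, 6 are failure with the IDR sub-label and 1 is failure without it. If that is wider than intended, the list can be narrowed without touching the primary rate.

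Optionally, add a sensitivity analysis in which the biopsy decides discordant cases.

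The cost is a wording amendment in four places, with no new data or procedures. The drawback is that the strict rule may lower the reported control rate; the sensitivity analysis would show by how much.
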